7.6. Other Data Handling Rules

Missing data will not be imputed in listings. The listings will only present the data recorded on the original Case Report Form.

If an AE has a completely missing onset date, then the AE will be considered a TEAE. A medication with a completely missing start date is considered a prior medication. A medication with a completely missing stop date is considered a concomitant medication.

If an AE or a medication has a partial missing start date or stop date, the following rules will be used to determine whether it is a TEAE, or a prior or concomitant medication.

Table 21: Partial Date Imputation Rule for TEAE or Medication

Partial Missing Start or Stop Date	Derived Start Date	Imputed Stop Date
Missing month and day, and the year is present	January 1 of that year or first dose date if the year is the same as the year of first dose date	December 31 of that year
Missing day, but year and month are present	First day of that month or first dose date if the year and month are the same as the year and month of first dose date	Last day of that month
Missing month, but year and day are present	Missing month derived as January or same as first dose month if the year is same as the year of first dose.	Missing month imputed as December

A date with a missing year will be considered as a completely missing date, and no imputation rule will be applied.

The rules described in [Table 21](#) is also used for determining the cycle of AE and concomitant medication. The derived date is used for determining TEAEs, the cycle of AE, and concomitant medication.

For medical history, pre-study surgery, prior radiotherapy, and prior systemic anticancer therapies, a partial missing start date will be imputed as below:

1. Missing year :no imputation, date left missing

2. Missing day and month : January 1 will be assigned to the missing fields.
3. Missing month only: Treat day as missing and replace both month and day with January 1.
4. Missing day only: Assign the first day of the month to the missing day.

Note: Additional rules for prior systemic anticancer therapies may apply as they pertain to checking for protocol violations

For medical history, pre-study surgery, prior radiotherapy, and prior systemic anticancer therapies, a partially missing stop date will be imputed as below:

1. Missing year : no imputation, date left missing
2. Month is missing and year is prior to year of first dose of study drug:impute 'December'.
3. Month is missing and year is the same as the year of the first dose of study drug: impute same month as in first dose date of study drug.
4. Day is missing: impute 'last day of that month'. If results in a date \geq the date of the first dose of study drug impute day as the day prior to date of first dose of study drug.

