9. SAFETY EVALUATIONS

9.1. Adverse Events

An AE is defined as any untoward medical occurrence in a clinical study patient and does not necessarily have a causal relationship with the study drug. An AE can therefore be any unfavorable and unintended sign (including an abnormal finding), symptom, or disease temporally associated with the use of a study drug, whether or not related to the study drug. This includes any occurrence that is new in onset or aggravated in severity or frequency from the baseline condition, or abnormal results of diagnostic procedures, including laboratory test abnormalities. For this study, progression of the cancer under study is not considered an AE unless the Investigator deems it related to study drug.

All AEs will be collected from the time informed consent has been documented through 30 days after the last dose of any study drug (safety follow-up) or until the start of new antitumor therapy, whichever is earlier. Any untoward medical event that occurs after the safety follow-up is not considered an AE, unless the Investigator considers that the AE is related to the study drug.

Signs and symptoms of a preexisting disease should not be considered an AE, but should rather be considered baseline signs and symptoms. Clinically significant worsening of preexisting signs and symptoms is considered an AE.

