5.6.2.2. Adverse Events

An AE is any untoward medical condition that occurs in patients while participating in this clinical trial. AEs will be coded according to the MedDRA (the most up-to-date version at the time of analysis) terminology and the severity of the toxicities will be graded according to NCI CTCAE Version 5.0, where applicable.

A treatment-emergent AE (TEAE) is defined as an AE that is starting or worsening at the time of or after the first dose of study drug administration and within 30 days after the last dose of study drug, and does not necessarily have a causal relationship to the use of the study drug.

In this study, only TEAEs will be summarized. Note that all collected AEs, including TEAEs, will be presented in listings as described in Section 5.1.

The following summary tables will be generated:

1. Summary of AEs with the number and percentage of patients reporting AEs, serious AEs, grade ≥ 3 AEs, AEs leading to study drug discontinuation, interruption and dose reduction, and AEs with the outcome of death.
2. Summary of treatment-related AEs with the number and percentage of patients reporting AEs, serious AEs, grade ≥ 3 AEs, AEs leading to study drug discontinuation, interruption and dose reduction, and AEs with outcome of deaths.
3. Summary of AEs by worst CTC Grade (grade 1, 2, 3, 4, 5, any grade, Grade ≥ 3) presented by SOC and Preferred Term (PT).
4. Summary of TEAEs by worst CTC grade (Grade 1, 2, 3, 4, 5, any grade, Grade ≥ 3) presented by SOC and PT.
5. Grade ≥ 3 AEs by worst CTC Grade (grade 3, 4, 5, 3-5) presented by SOC and PT.
6. Grade ≥ 3 TEAEs by worst CTC Grade (grade 3, 4, 5, 3-5) presented by SOC and PT.
7. Summary of AEs leading to death by SOC and PT.
8. Summary of the most common AEs ($\geq 10\%$ incidence) and median time to first AE by SOC and PT.

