7.2. Post-Baseline Period

To allow differentiation as to which study period an AE occurred, three categories are defined based upon onset date. AEs that have onset dates prior to the first dose of study drug are considered "prior." AEs with onset dates on or after the first dose of study drug and within 30 days following the last dose of study drug are considered "on-treatment" or equivalently "treatment emergent.". Events with onset dates more than 30 days after the last dose of study drug are considered "post-treatment." No "subtracting rule" will be applied when an AE occurs both pre-treatment and post-treatment with the same preferred term and grade. AE summary tables will be based on on-treatment AEs only. AEs with onset dates prior to the first dose of study drug as well as those after the last dose of study drug +30 days will be identified in the data listings.

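### SAP 7.6 and Table 21 can put AEs with partial or missing start dates on the wrong side of the treatment-emergent line, because the rules ignore the stop date and one row has no floor at first dose

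*SAP*

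**What the plan says.** SAP 7.6 and Table 21 give four rules for an AE start date that is not fully recorded.

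- Day missing: "First day of that month or first dose date if the year and month are the same" as those of first dose.
- Month and day missing: "January 1 of that year or first dose date if the year is the same as the year of first dose date".
- Month missing, day present: "Missing month derived as January or same as first dose month if the year is same as the year of first dose". The recorded day is kept.
- Nothing recorded: "If an AE has a completely missing onset date, then the AE will be considered a TEAE".

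Table 21 also imputes partial stop dates, in each case to the latest date that the missing fields allow. No start-date rule refers to that column. The SAP then says "The derived date is used for determining TEAEs, the cycle of AE, and concomitant medication".

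The line that these dates are compared with is in two places. SAP 5.6.2.2 defines a TEAE as an "AE that is starting or worsening at the time of or after the first dose of study drug administration", up to 30 days after the last dose. SAP 7.2 treats as on-treatment "AEs with onset dates on or after the first dose of study drug and within 30 days following the last dose of study drug", and confines the AE summary tables to those events.

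Pre-dose AEs are foreseen. Protocol 9.1 says "All AEs will be collected from the time informed consent has been documented through 30 days after the last dose" (or until new antitumor therapy, if earlier), and Protocol Table 1 places screening within 28 days of first dose. SAP 7.1 and 7.2 both define a pre-treatment class of AE.

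**The concern.** Moving an incomplete AE start to the first dose is a sound default when the record leaves the answer open, because it avoids losing a possible treatment-emergent event. It is not sound when the stop date shows that the event was over before dosing. Such an AE neither started nor worsened on treatment, yet the written rule puts it in the TEAE tables.

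The month-missing row works the other way. It can give a derived date before first dose and so remove an event that may well have begun on treatment. A record with more date information is then treated less cautiously than one with less.

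All AE summary tables rest on this classification, and the derived date also sets the AE cycle. A programmer must either code a start later than its own stop or depart from the SAP without documentation.

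**Working it through.** The documents give no figure to reproduce, so the check applies the Table 21 rules literally and compares each derived start with first dose, as SAP 7.2 and 7.6 direct. The dates are illustrative. All fall in one calendar year, and ?? marks a missing field.

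| Recorded start | Stop | First dose | Derived start | Class under SAP 7.6 | What the record shows |
|---|---|---|---|---|---|
| ??-March | 10 March | 15 March | 15 March | TEAE | Ended 5 days before first dose |
| ??-?? | 10 March | 15 March | 15 March | TEAE | Ended 5 days before first dose |
| wholly missing | 10 March | 15 March | none | TEAE | Ended 5 days before first dose |
| ??-February | 10 March | 15 March | 1 February | Pre-treatment | Correctly placed |
| 05-?? | none | 20 March | 05 March | Pre-treatment | Undetermined |
| ??-?? | none | 20 March | 20 March | TEAE | Undetermined |

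The first three rows conflict with the SAP's own TEAE definition. In the first two, the derived start is also 5 days after the stop (15 − 10). The last two rows differ only in whether the day is known, and the record with the day known is the one left out.

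**How often the rules would bite, given such a record.** Assume first-dose dates spread evenly over a 365-day year.

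*AEs that truly start 1 to 28 days before first dose.* There are 365 × 28 = 10,220 combinations of first-dose date and onset date.

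- Day missing: the start moves to first dose when onset falls in the first-dose month. For first-dose day D this covers min(D − 1, 28) onset days. Summed over a month, that is 462 for 31 days, 434 for 30 days and 378 for 28 days. The total is 7 × 462 + 4 × 434 + 378 = 5,348, and 5,348 / 10,220 = 52%.
- Month and day missing: the start moves unless onset falls in the previous year, which happens in 28 + 27 + … + 1 = 406 combinations. (10,220 − 406) / 10,220 = 96%.

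A known stop date before first dose changes neither share. The result is a demonstrable error only where such a stop date exists.

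*AEs with only the month missing that truly start on treatment in the first-dose year.* The derived date falls before first dose when the recorded day is earlier than the first-dose day D. With days spread evenly over a 30-day month the share is (D − 1)/30:

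- D = 1: 0%
- D = 15: 14/30 = 47%
- D = 28: 27/30 = 90%

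Enumerating the 365 first-dose dates gives 42% if onset is within 28 days of first dose, and 44% if within 168 or 365 days.

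**After the change proposed below.** The first three rows become pre-treatment, with no start later than 10 March. The fourth is unchanged. In the fifth, the later of 05 March and 20 March is 20 March, so the AE is a TEAE and agrees with the sixth. If the fifth carried a stop of 10 March, it would be pre-treatment.

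**The case against.** The case for leaving the rules alone is that defaulting to TEAE is the usual conservative convention and that few records are exposed. Protocol 9.2.1 asks for onset and resolution dates, Protocol 12.6.2 has monitors verify eCRF entries against source, and a date with the day known but the month missing is an unusual pattern. Nothing disappears either: all AEs are listed, pre-dose AEs are identified there, and listings show the dates as recorded. All of this stands, and it keeps the severity low. It does not defend a rule that overrides a recorded stop date. The SAP already uses a check of this kind elsewhere in 7.6, where an imputed prior-therapy stop date on or after first dose is moved to the day before it.

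Four stronger readings are tempting, and the documents do not support them.

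- A reader might infer that every AE with a partial start and a pre-dose stop is misclassified. The fourth row of the table shows otherwise: a February start with first dose in March is placed correctly.
- A reader might infer that impossible dates flow into time to onset, clustering and time to resolution of AEs of special interest. SAP 7.6 ties the derived date to TEAE status, AE cycle and concomitant medication. SAP 7.4 and 7.5 do not refer to Table 21.
- A reader might take the day-05, 20 March example as a 9-in-10 chance of error, because 9 of the 10 possible dates that year (05 March, then 05 April to 05 December) follow first dose. That counts calendar dates for one chosen case and assumes treatment lasts long enough. First dose on 20 November gives 1 of 2, and on 20 December 0 of 1.
- A reader might say that the month-missing row contradicts recorded data. With the month unknown and no informative stop date, the data do not settle the matter. The fault there is an inconsistent, anti-conservative default.

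**Conclusion.** The rules are wrong as written, with low severity. Ignoring the stop date can admit to the TEAE tables an AE that the record shows had ended before dosing, against SAP 5.6.2.2 and 7.2. Having no floor in the month-missing row can leave out an AE that would have been kept with less date information.

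The size is conditional. The documents do not say how many AEs have partial dates; that the number is small, and smallest for the month-missing pattern, is an assumption. The percentages above further assume evenly spread dates and describe what happens to such a record, not how often one occurs. The AE summary tables and the AE cycle are affected. Response and survival endpoints are not.

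**What to change.** Add two sentences to SAP 7.6, Table 21:

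1. If the AE stop date, recorded or imputed, is before the first dose date, the AE is not a TEAE and its derived start may not be later than the stop date. This overrides the rule for a completely missing onset.
2. If only the month of the start is missing and the year is that of first dose, use the later of the derived date and the first dose date, subject to (1).

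The first sentence is safe because Table 21 imputes a partial stop to the latest date that the missing fields allow; if even that date precedes first dose, the AE had ended. Where the stop date is wholly missing, or falls on or after first dose, the conservative default remains. The cost is the two sentences and a few lines of code, with no new data to collect.
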